9. MEASUREMENT OF EFFECT

9.1. Response Review:

The Data Safety Monitoring Committee will review the responses to the primary and secondary objectives every 6 months during the trial.

9.2. Response Criteria:

9.2.1. The primary objective will be measured by recording the daily symptoms experienced by the subjects and the number of subjects with no clinical symptoms during 6 g peanut flour challenge at time 50 weeks compared to time 0 weeks. The change in tolerated dose will be assessed between baseline and one year. The proportion of patients who tolerate 6 g of peanut flour will be compared at baseline and at the one year point using McNemar's test for matched pair data. The proportion of subjects will be estimated with exact binomial confidence intervals.

9.2.2. For the first secondary objective, flow cytometric analysis of T, NKT cells, and basophils will be performed through the measurement of the percent of cells producing a

cytokine as well as measuring surface and intracellular markers expressed upon activation and the significance of changes from time 0 to 1 year will be assessed as described below by using a paired t-test of the log-transformed data. Baseline measures of cell activation will be summarized by means with standard deviation. Normality will be assessed by quantile-quantile plots, and non-normality will be addressed by data transformations. A general linear mixed model will be used to estimate the effect of the therapeutic procedure over time. The model will include a fixed effect for time (discrete), and the matrix of correlated error terms will assume a first-order autoregressive structure. Alternative correlation structures such as the unstructured and compound symmetry will be considered. Correlation structures will be assessed by Akaike's Information Criteria. The likelihood ratio test will be used to test for overall significance of the model. P-values will be adjusted using the Holm's step down Bonferonni correction for multiple comparisons. Activation responses that are significant at the 0.05 level after adjustment will be further assessed. Pairwise comparisons between discrete time points will be tested for significant differences, and p-values will be adjusted using the Bonferonni correction. Statistical significance of the adjusted p-values will be assessed at the 0.05 level.

Spearman rank correlations will be estimated for all pairwise comparisons between activation responses. P-values for testing for significant correlations will be adjusted using Bonferonni's correction for multiple comparisons. Partial correlation coefficients will also be estimated for all activation responses adjusting for subject-level effects across all time points.

- 9.2.3. The second secondary objective will be assessed by recording the number of episodes of prior viral infection symptoms experienced after symptomatic daily peanut dosing. This number will be compared to the episodes of symptomatic daily peanut dosing with no prior viral infection symptoms. The proportion of subjects will be estimated with exact binomial confidence intervals. This analysis will also be used to determine the proportion of symptomatic daily doses with preceding symptoms of viral infection compared to non-viral associated symptomatic daily doses.
- 9.2.4. The third secondary objective will be assessed by the comparison of amount of peanut protein tolerated at the 24 month food challenge to the 25 month food challenge using McNemar's test for matched pair data.

[figure not shown]

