Given the risk of clinical reactions to peanut allergen with accidental unintentional exposures and the impact of peanut avoidance on the quality of life of peanut allergic subjects (21), peanut immunotherapy as an effective treatment is an unmet need. This effective therapeutic procedure with an acceptable safety profile is needed in more academic centers around the country. Subjects receiving this therapy need close monitoring through expert centers to treat potential systemic symptoms. The immune determinants of clinical tolerance are still not completely understood. The goal of this proposed trial is to utilize the efficacy of oral immunotherapy to study the safety of peanut oral immunotherapy and evaluate immune mechanisms of clinical tolerance, using technology to identify T cell cytokine responses and subsets by flow cytometry. This trial will also expand the availability of this therapy to subjects in the southern United States.

All subjects will receive the peanut protein intervention. There is no placebo control for this study. In order to meet inclusion criteria subjects will not be able to tolerate a 1 gram peanut protein challenge. The primary outcome to be studied is the safety of the therapy and the secondary outcome will include changes in T and NKT cell function and intracellular cytokine expression from peanut allergic subjects during peanut OIT. We will look at both the initial response to building up the dose and changes during the maintenance phase. We are requesting a target enrollment of 15 subjects. Subjects will be recruited from the Texas Children's Hospital Allergy and Immunology Clinic. Subjects are expected to participate for a total of 38 months. After screening visits, the study will require approximately 33 visits with 2 phases: the build-up phase (weeks 0-50), followed by the maintenance phase (2 years).

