2. OBJECTIVES

2.1 *Primary Objectives:*

- 2.1.1. The primary objective is to determine whether peanut oral immunotherapy safely develops clinical tolerance in peanut allergic patients by assessing the change of dose tolerated and to determine the percentage of subjects who can tolerate 6 g of peanut flour with absence of clinical symptoms during a food challenge following the initial desensitization phase of peanut flour which includes a 50 week dose escalation phase and 104 week maintenance phase on a peanut equivalent dose.

2.1. Secondary Objectives:

To determine the immune mechanisms of clinical tolerance, using technology to identify T cell cytokine responses and subsets, as well as basophil activation responses as measured by flow cytometry. T and NKT cell function and intracellular cytokine expression will be measured.

2.2.1. To determine whether viral exposure potentiates response to in vitro peanut allergen exposure and to assess those changes during peanut OIT.

2.2.2. To compare the change in dose tolerated after one month of abstaining from peanut to determine sustained unresponsiveness.

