- Targeted History and Physical Exam and Diet History: A brief medical and diet history will be obtained and a focused physical exam will be performed.
- Review Home Symptom Diary: At each visit we will review any symptoms experienced while taking the food protein.
- Epinephrine injector will be checked for expiration date and parents/guardian will demonstrate proper use.
- Dose Escalation: The subject must return in no less than 10 days after each visit to receive an increased amount of peanut protein. (See Table 3.) At each visit the subject will be given a slightly larger amount of peanut protein than he or she was receiving prior to that visit. After the first visit the subject will be taking at least the equivalent of approximately 1/100th of a peanut daily and once the subject gets to the maintenance dose he or she will be taking the equivalent of approximately 15 peanuts daily. The length of time the participant is in the build-up phase is dependent on the starting dose determined from DBPCFC and how well each subsequent buildup dose is tolerated. The subject will build up to 3.9 grams of peanut protein or the highest dose tolerated. This is known as the maintenance dose.

Table 3. Dose Escalation Table

Weeks On OIT	Dose No.	Protein Per Soufflé portion cup (mg)	PN flour weight per soufflé portion cup (mg)
0,1	1	1.8	3.6
2,3	2	3.6	7.2
4,5	3	7.2	14.4
6,7	4	14.4	28.8
8,9	5	28.8	57.6
10,11	6	40	80
12,13	7	60	120
14,15	8	80	160
16,17	9	100	200
18,19	10	120	240
20,21	11	240	480
22,23	12	300	600
24,25	13	450	900
26,27	14	600	1200
28,29	15	750	1500
30,31	16	900	1800
32,33	17	1050	2100
34,35	18	1200	2400
36,37	19	1350	2700
38,39	20	1500	3000
40,41	21	1800	3600
42,43	22	2100	4200
44,45	23	2400	4800
46,47	24	3000	6000
48,49	25	3600	7200
50,51	26	3900	7800

6.5. Follow-up Visits (every 6 months for 24 months after maintenance dose is reached) (approximately 3 hour per visit):

Once the maintenance dose is achieved, the patient will follow up in the clinic 2 weeks later to ensure the higher dose is being tolerated and will switch to a peanut equivalent

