dose (Table 4). The first dose of the peanut equivalent will be given in the hospital setting. The family will be instructed on how to administer peanut equivalent dose. The subject will continue to follow the “Instructions for Daily Home Doses” as used for peanut flour dosing. This will be considered “Month 0”. The participant will remain on this dose for 24 months and follow-up visits will occur every 6 months. The subject will continue to follow the peanut flour dosing guidelines. A food challenge will be performed within 1 month of the “Month 0” visit.

Table 4. Peanut Equivalent Dose

Peanut Product	Peanut Protein (gram) /serving	Maintenance Dose (3900mg peanut protein)	Alternative Dose (if maintaining below 3900mg)
Creamy Peanut Butter *Peter Pan or Reese’s Creamy Peanut Butter*	8 grams=2 Tablespoons	1 Tablespoon	1300 mg =1 teaspoon 325mg=0.25 teaspoon
JIF Peanut Powder	8 grams=3 Tablespoons	1.5 Tablespoons	
PB2 Powdered Peanut Butter (Bell Plantation)	5 grams=2 Tablespoons	1.5 Tablespoons	1300 mg= 1.5 teaspoon 300 mg = 3/8ths of a teaspoon
Dry Roasted Peanuts	0.175 grams=1 peanut	22 peanuts	1300 mg = 7 and ½ peanuts 350 mg = 2 peanuts
Peanut M&M’s	0.15 grams=1 piece	26 pieces	1300 mg = 8 and 2/3 pieces 300 mg=2 pieces
Reese’s Pieces Candy	0.078 grams=1 piece	50 pieces	1300 mg = 16 and 2/3 pieces 312 mg = 4 pieces
Reese’s Peanut Butter Cups Miniatures	0.8 grams=1 miniature cup	~5 miniature cups	1300 mg = 1 and 5/8 th cups 300 mg = 3/8 th cup

Other approved alternative:			
-----------------------------	--	--	--

- If the subject experiences no adverse events with the maintenance dose or highest dose tolerated after 1 month, the provider will have the option of decreasing the observation period at home to 1 hour. The subject will need to avoid any form of physical activity 2 hours after ingestion.
- Peak Flow: Peak flow measures will be accepted with results >90% of predicted.
- Amount of blood to be drawn: After maximum tolerated dose is achieved at approximately 1 year (drawn at Visit 30- Month 0 DBPCFC) and every 6 months afterwards, we will draw up to 4-6 tablespoons of blood (based on the subject's weight) for peanut-specific IgE, IgG, and IgG4, cellular immune studies and basophil histamine release assays until the end of the protocol.
- Allergy Skin Prick Tests (PST): Endpoint dilution skin testing to peanut will be done at month 0 and month 12 visits.

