Peanut equivalent will be used for the food challenge at 0 month maintenance food challenge. The challenge will consist of increasing doses of peanut (in the form of peanut equivalent) given every 15 minutes in increasing amounts (Table 5). The other challenge will consist of placebo material given also in increasing doses. The highest dose will be equivalent to approximately 34 peanuts.

- Review Home Symptom Diary: We will review any symptoms experienced while taking the food protein.
- Urine Pregnancy Test: For females of reproductive potential a urine pregnancy test will be performed prior to the food challenge. If the subject is pregnant the food challenge will not be performed and the subject will be dismissed from the study.

Table 5

0 Month Maintenance Phase Double-Blinded Placebo Controlled Food Challenge Protocol		
Dose Number	Approximate Dose Amount (PEANUT PROTEIN)	Cumulative Dose Amount (peanut protein)
1	75 mg	75 mg
2	150 mg	225 mg
3	500 mg	725 mg
4	1000 mg	1725 mg
5	2000 mg	3725 mg
6	3000 mg	6725 mg
7	4000 mg	10725 mg
8	4500 mg	15225 mg
9	5000 mg	20225 mg
10	6000 mg	26225 mg

6.7. End of Study Food Challenge Visits (24 and 25 months after maintenance dose is reached) (approximately 8 hours per visit):

- Amount of blood to be drawn: At both visits, we will draw up to 4-6 tablespoons of blood (based on the subject's weight) for peanut-specific IgE, IgG, and IgG4, cellular immune studies, and basophil histamine release assays
- Allergy Skin Prick Tests (PST): Endpoint dilution skin testing to peanut will be done at the month 24 and month 25 visit.
- Spirometry or Peak Flow: Spirometry will be attempted in all participants. If valid spirometry results are not successfully obtained, the attempt is documented and peak flow measures will be accepted for the entry criteria with results >90% of predicted. For participants that are able to complete spirometry, FEV1 must be greater than 90% predicted on the day of the challenge to participate in the food challenge.
- Targeted History and Physical Exam and Diet History: A brief medical and diet history will be obtained and a focused physical exam will be performed.
- DBPCFC: The subject will come to Texas Children's Hospital in Houston for a Double Blind Placebo Controlled Food Challenge (DBPCFC) to the study protein (peanut) to determine if he or she is still allergic to peanut or can tolerate peanut.

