The DBPCFC visit will last approximately 9 hours. The food challenge may be performed in one day or split into two days. The subject will discontinue antihistamines (for example Zyrtec or Claritin) for 7 days before the procedure and must be off oral corticosteroids for one month before the food challenge.

Peanut equivalent will be used for the food challenge. The challenge will consist of increasing doses of peanut (in the form of peanut flour and mixed with juice or baby food) given every 15 minutes in increasing amounts (Table 6). The other challenge will consist of placebo material given also in increasing doses. The highest dose of peanut flour will be equivalent to approximately 34 peanuts.

They will return 4 weeks after the 24 month food challenge for the 25 month food challenge. It will be conducted in the same manner as the 24 month food challenge. During this 4 week interval the subject must avoid peanut in his or her diet and will not take any peanut protein as he or she had been doing previously.

- Review Home Symptom Diary: At the 24 month visit we will review any symptoms experienced while taking the food protein.
- Urine Pregnancy Test: For females of reproductive potential a urine pregnancy test will be performed prior to the food challenge at both the 24 month and 25 month visits. If the subject is pregnant the food challenge will not be performed and the subject will be dismissed from the study.

Table 6.

24 and 25 Month Maintenance Phase Double-Blinded Placebo Controlled Food Challenge Protocol
--

Dose Number	Approximate Dose Weight (PEANUT PROTEIN)	Cumulative Dose Weight (peanut protein)
1	75 mg	75 mg
2	150 mg	225 mg
3	500 mg	725 mg
4	1000 mg	1725 mg
5	2000 mg	3725 mg
6	3000 mg	6725 mg
7	4000 mg	10725 mg
8	4500 mg	15225 mg
9	5000 mg	20225 mg
10	6000 mg	26225 mg

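### The primary tolerance endpoint fixes neither the dose nor the visit: 6 g of flour can mean step 5, 6 or 10 of the challenge tables, and Sections 2.1.1 and 9.2.1 point to challenges about two years apart

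*Combined protocol and SAP*

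**What the plan says.** Section 2.1.1 aims to "determine the percentage of subjects who can tolerate 6 g of peanut flour with absence of clinical symptoms during a food challenge", and places that challenge "following the initial desensitization phase of peanut flour which includes a 50 week dose escalation phase and 104 week maintenance phase". Section 9.2.1 measures the same objective by the "number of subjects with no clinical symptoms during 6 g peanut flour challenge at time 50 weeks compared to time 0 weeks". It then compares the proportions at baseline and one year with McNemar's test and adds exact binomial intervals.

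No challenge is scheduled at week 50. The nearest is the month 0 challenge, and the blood-draw item in Section 6.5 ties the one-year point to it: "After maximum tolerated dose is achieved at approximately 1 year (drawn at Visit 30- Month 0 DBPCFC". The later challenges are at months 24 and 25 of maintenance (Section 6.7).

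Tables 5 and 6, which define the month 0 and month 24/25 challenges, list doses in mg of peanut protein only and are identical. On the material given, Section 6.6 says "Peanut equivalent will be used for the food challenge at 0 month maintenance food challenge". Section 6.7 first says peanut equivalent, then describes flour mixed into juice or baby food, and adds: "The highest dose of peanut flour will be equivalent to approximately 34 peanuts".

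**The concern.** A responder definition needs a dose, a unit, a basis (single or cumulative) and a visit. Here the unit in the endpoint does not match the unit in the tables that measure it, the basis is not stated, and the two sections defining the endpoint name different times.

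The proportion, its exact interval and the McNemar result all depend on these choices. Section 9.1 has responses to the primary and secondary objectives reviewed every 6 months, so results under each reading could be known before one is chosen. The sample is small: 15 enrolled, with 10 required and 50% attrition assumed in Section 10.1.

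Baseline data do not narrow the choice. Section 1 states that "In order to meet inclusion criteria subjects will not be able to tolerate a 1 gram peanut protein challenge", so no enrolled child can count as a baseline pass at a higher threshold.

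**Working it through.** **1. The plan's own figures reproduce.** Running sums of the dose column in Tables 5 and 6 (75, 150, 500, 1000, 2000, 3000, 4000, 4500, 5000, 6000 mg) give 75, 225, 725, 1725, 3725, 6725, 10725, 15225, 20225 and 26225 mg, as printed. Table 3 has 26 doses at two-week steps, so a child starting at dose 1 reaches dose 26 at (26 − 1) × 2 = 50 weeks.

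**2. Unit.** Flour to protein is 2:1 in every row of Tables 2 and 3, so 6000 mg flour = 3000 mg protein (Table 3, dose 24). That is below the 3900 mg protein target for maintenance, although some children maintain at less.

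**3. Which step is 6 g?** For each reading, take the first step whose single or cumulative dose reaches the target.

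| Reading of 6 g | Target (mg protein) | Step | Cumulative protein at that step (mg) |
|---|---|---|---|
| Flour, cumulative | 3000 | 5 | 3,725 |
| Flour, single dose | 3000 | 6 | 6,725 |
| Protein, cumulative | 6000 | 6 | 6,725 |
| Protein, single dose | 6000 | 10 | 26,225 |

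Spread in cumulative protein: 6725/3725 = 1.8 within the flour wording; 26225/3725 = 7.0 across all readings. A child who first reacts at step 6 passes only if the threshold is step 5. A child who first reacts at steps 7 to 10 passes at steps 5 and 6 but fails at step 10.

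**4. Why the protein readings cannot be dismissed.** Section 6.7 equates the top step with about 34 peanuts and calls it flour. At Table 4's 0.175 g protein per peanut, 34 × 0.175 = 5.95 g protein, and 6000/175 = 34.3 peanuts. Six grams of flour would be 3000/175 = 17.1 peanuts. So on Table 4's figure, Section 6.7 labels a 6 g protein dose as flour.

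**5. Visit.** Section 2.1.1: 50 + 104 = 154 weeks, which corresponds to Visit 34. Section 9.2.1: 50 weeks or one year, which corresponds to Visit 30. The difference is 104 weeks.

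Week 50 is also not a common time point, because "The length of time the participant is in the build-up phase is dependent on the starting dose determined from DBPCFC". At two-week steps without holds:
- 1.8 mg start (dose 1): 25 × 2 = 50 weeks
- 750 mg start (dose 15): (26 − 15) × 2 = 22 weeks

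Adding 2 weeks to the month 0 visit and up to about 4 more to the challenge puts Visit 30 at about weeks 52–56 and 24–28 respectively. Section 6.4 allows escalation visits as close as 10 days apart; build-up would then take 25 × 10 = 250 days (about 36 weeks) or 11 × 10 = 110 days (about 16 weeks).

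**6. Effect on the test.** The entry challenge (Table 2) totals 2000.5 mg protein, or 4,001 mg flour, with a largest single dose of 2,000 mg flour. Six grams of flour is never given at baseline. With no baseline passes, all discordant pairs go one way, and for m later passes the two-sided exact McNemar p = 2 × 0.5^m:
- m = 5: 0.0625
- m = 6: 0.03125

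Exact (Clopper–Pearson) 95% intervals for assumed counts:

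| Passes | 10 assessed | 15 assessed |
|---|---|---|
| 6 | 60% (26.2–87.8) | 40% (16.3–67.7) |
| 5 | 50% (18.7–81.3) | 33% (11.8–61.6) |

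**The case against.** **The flour wording is explicit.** Sections 2.1.1 and 9.2.1 both say flour, and the 2:1 ratio is uniform. Read literally, the threshold is 3 g protein and only steps 5 and 6 remain; step 10 requires flour to be read as protein. The peanut counts supporting that reading are not consistent: Section 6.3 implies 0.25 g per peanut (1 g protein as 4 peanuts) and Section 6.4 about 0.26 g (3.9 g as 15). At 0.25 g, 34 peanuts is 8.5 g protein, which matches no step. This stands as a limit on step 10, but the literal wording still leaves two steps open.

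**The 7.0-fold figure uses the widest measure.** The nominal thresholds differ 2-fold (3 g against 6 g protein), and the largest single doses at steps 5 and 10 differ 3-fold (2,000 against 6,000 mg). This is correct. The ratio describes cumulative exposure only.

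**The change in significance depends on assumed counts.** It occurs only between 5 and 6 passes. Section 1 cites an open-label study in which over 90% tolerated 3900 mg; with 9 passes p = 0.004, and losing one child (8 passes, p = 0.008) changes nothing. This stands for the p-value. It does not protect the reported proportion, and the cited rate does not cover 6,725 or 26,225 mg cumulative.

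**Section 9.2.1 is the analysis section and consistently points to one year**, while the month 24 challenge already has a secondary role in Sections 2.2.2 and 9.2.4. The visit repair may therefore fall mainly in Section 2.1.1. That makes it easier, but the two sections still cannot both be followed.

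**This is only part of the primary objective.** Section 1 names safety as the primary outcome, Section 9.2.1 lists daily symptoms first, and the sample size rests on interferon-gamma. All true, but the tolerance proportion is the only primary measure given a named test and an interval.

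**Conclusion.** The concern holds. The visit conflict and the missing single-or-cumulative basis can be read directly from the text. The unit conflict follows from the protocol's own 2:1 ratio and its protein-only challenge tables.

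On the narrowest reading, two steps (1.8-fold in cumulative protein) and two visits about two years apart remain open. Allowing the flour label that Section 6.7 puts on the top step, there are three steps and a 7.0-fold range; that wider range relies on Table 4's 0.175 g per peanut. The p-value change is an illustration at 5 against 6 passes, not a prediction. The change in tolerated dose, also listed in Section 9.2.1, does not depend on the 6 g threshold but shares the visit conflict.

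Because this concerns the definition of a primary endpoint, it must be settled before analysis.

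**What to change.** Reconcile Sections 2.1.1 and 9.2.1 with each other and with Tables 3, 5 and 6:

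1. State the threshold in mg of peanut protein, name the Table 5/6 step, and say whether it is a single or a cumulative dose.
2. Name one challenge, Visit 30 or Visit 34, as primary in both sections, and make the other a named secondary.
3. Replace the week 50 and one-year wording with the visit label.
4. Bring the flour and peanut-equivalent wording of Sections 6.6 and 6.7 into line with the protein units of their tables.

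Which threshold and which visit are intended is for the sponsor to decide.

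The cost is text only, since both challenges are already scheduled. If the chosen reading departs from the literal flour wording, it changes the primary endpoint and needs a dated amendment before analysis. The reported pass rate may be lower under the reading chosen, and one of the two challenges becomes secondary.

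### The primary responder threshold is set in grams of peanut flour while the challenge that measures it runs in protein, so the same challenge record can be classed more than one way

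*Combined protocol and SAP*

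**What the plan says.** Section 2.1.1 sets as part of the primary objective to "determine the percentage of subjects who can tolerate 6 g of peanut flour with absence of clinical symptoms during a food challenge". Section 9.2.1 uses the same amount and unit, counting the "number of subjects with no clinical symptoms during 6 g peanut flour challenge at time 50 weeks compared to time 0 weeks", then names the test: "The proportion of patients who tolerate 6 g of peanut flour will be compared at baseline and at the one year point using McNemar's test".

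On treatment, section 6.4 states: "The subject will build up to 3.9 grams of peanut protein or the highest dose tolerated". The last row of Table 3 (weeks, dose number, mg protein, mg flour) reads "50,51 26 3900 7800". Two rows earlier it reads "46,47 24 3000 6000".

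The challenges that supply the endpoint are in Table 5 (Month 0) and Table 6 (Months 24 and 25). Both list only mg of peanut protein, over ten identical steps from 75 mg to 6,000 mg. Section 6.6 says of this series: "The highest dose will be equivalent to approximately 34 peanuts". Section 6.7 gives the same peanut count for the top step of Table 6 but calls that amount peanut flour. Table 4 puts one dry roasted peanut at 0.175 g of protein.

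**The concern.** The endpoint is in one unit and the instrument in another, and the two differ by a factor of 2. Taken literally, 6 g of flour is an amount that a child at target maintenance already exceeds every day. Taken with section 6.7's loose use of the word flour, 6 g could instead mean the 6,000 mg protein top step, which lies well above the daily dose. No row of Table 5 or 6 is labelled as a 6 g flour step, and nothing says whether the amount is one portion or a running total.

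Two things are at stake. First, who counts as a responder depends on a reading that could be chosen after the challenge results are known. Second, the meaning of the percentage changes. On one reading it shows tolerance of something below the daily dose. On another it shows a margin above it.

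**Working it through.** **Unit conversion.** Flour divided by protein is 2.0 in every row of Table 2 and in the two Table 3 rows used here (6,000/3,000 and 7,800/3,900).

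- Threshold in protein: 6 g flour × 0.5 = 3.0 g, which is build-up dose 24 of 26.
- Target maintenance: 7.8 g flour × 0.5 = 3.9 g, which reproduces the plan's own figure.
- Ratio: 3.0 / 3.9 = 0.77.
- Top challenge step: 34 peanuts × 0.175 g = 5.95 g of protein. The peanut count in sections 6.6 and 6.7 therefore matches 6,000 mg of protein. Six grams of flour would be 3,000 / 175 = about 17 peanuts.

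**Prior exposure.** On the Table 3 schedule, doses 24, 25 and 26 (3,000, 3,600 and 3,900 mg protein) each last two weeks, and the switch to food at Month 0 follows. A child at target has then taken at least 3 g of protein daily for 3 × 2 = about six weeks.

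**Where each reading falls in Tables 5 and 6.** Cumulative totals are 725 mg after step 3, 1,725 after step 4, 3,725 after step 5, 6,725 after step 6 and 26,225 after step 10.

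| Reading of 6 g | Protein | Met at | Step dose / 3,900 mg | Cumulative / 3,900 mg |
|---|---|---|---|---|
| Flour, cumulative | 3,000 mg | step 5 | 0.51 | 0.96 |
| Flour, single dose | 3,000 mg | step 6 | 0.77 | 1.72 |
| Protein, cumulative | 6,000 mg | step 6 | 0.77 | 1.72 |
| Protein, single dose | 6,000 mg | step 10 | 1.54 | 6.72 |

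The four readings give three different cut points. A child who completes step 5 and reacts at step 6 is a responder only on the cumulative flour reading. A child who completes step 6 and reacts anywhere from step 7 to step 10 is a responder on every reading except the single-dose protein one.

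**Effect on the primary test.** The entry challenge (Table 2) stops at a 2 g flour portion, about 4.0 g of flour cumulatively, and entry requires a reaction. Baseline responders are therefore zero by design. With b responders at one year, the exact two-sided McNemar p-value is 2 × 0.5^b:

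- b = 5: p = 0.063
- b = 6: p = 0.031

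One reclassified child can move the result across 0.05. One child is 1/15 = 6.7 percentage points of those enrolled. At the plan's 50% attrition, 7 or 8 children remain, and one child is 1/7 = 14.3 or 1/8 = 12.5 points.

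**The case against.** A reader might infer that the literal threshold makes the primary result a restatement of who finished build-up. The documents do not support that strength of claim, for these reasons:

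- Reaching the 3,000 mg step means five earlier doses at 15-minute intervals and a cumulative 6,725 mg, which is 1.72 times the target daily dose.
- Section 6.6 requires seven days off antihistamines before the challenge. Section 6 otherwise allows them during the study.
- The endpoint requires absence of symptoms, whereas Appendix II continues daily dosing after a first Grade 1 reaction. A child can finish build-up and still fail. Against this, a second reaction triggers a hold and re-challenge, so completers are to some degree selected for tolerance.
- Daily doses follow a snack (section 6.2). Sections 6.6 and 6.7 mention none for the challenge.
- Some children will be maintained below 3 g of protein. For them the threshold lies above the daily dose.

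The extent of overlap cannot be computed from the documents.

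It can also be said that change in tolerated dose is already in 2.1.1 and 9.2.1 and uses every step, so evidence above the daily dose is collected. That stands, but the proportion tested by McNemar does not use it.

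Finally, section 6.7 suggests that flour may simply be a slip for protein. That is plausible. It does not remove the point, because the plan would then state its primary threshold in the wrong unit.

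**Conclusion.** The point holds as a conflict of unit and definition. The primary responder threshold, as written, is 3 g of protein and below the 3.9 g target daily dose. The challenge and its peanut count point to 6 g of protein as the top step. The candidate readings run from step 5 to step 10, and the two single-dose readings are four steps and a factor of 2 apart. In a study of 15 children this can change the primary proportion and the test result, so it is more than missing detail.

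If flour is meant literally, the proportion may add little beyond build-up completion for children at full maintenance. It is not fixed in advance, for the reasons above. Nor do the documents show that the threshold has to lie above the daily dose. If flour was intended, a higher bar would be a preference.

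The conclusion rests on the 2:1 flour-to-protein ratio and 0.175 g of protein per peanut, both from the protocol, and on zero baseline responders, which follows from the entry criteria. It does not depend on which follow-up challenge is used, since Tables 5 and 6 have the same steps.

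**What to change.** Before data are analysed, reconcile sections 2.1.1 and 9.2.1 with Tables 5 and 6. State the responder threshold in mg of peanut protein, say whether it is a single or cumulative amount, and name the table step it denotes. Align the flour wording in section 6.7 with Table 6.

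Report the proportion completing each challenge step without symptoms, with exact binomial confidence intervals, so that results below and above the daily dose are both visible.

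If flour was truly intended, keep that threshold, state that it lies below the target daily dose, and do not interpret it as a margin above that dose.

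The cost is a text amendment and one extra table from data already collected. No visit, procedure or challenge dose changes. The downside is that the reported responder percentage may be lower if the 6,000 mg protein step was intended.
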